6.1 Mother Screening Visit

The Screening Visit may take place up to two weeks prior to the Entry Visit. Multiple visits may be conducted within this timeframe to complete all required procedures, if necessary. Written informed consent will be obtained before any study-specific screening procedures are performed. For potential participants who do not meet the eligibility criteria, screening may be discontinued once ineligibility is determined. A Screening Failure Results CRF must be completed for any mother-infant pair who screen but do not enroll for any reason. Ineligible women may rescreen for study participation at a later time.

Mother Screening Visit Procedures (up to 2 weeks prior to enrollment)	
Administrative and Regulatory	
 • Obtain written informed consent • Obtain screening number from SES • Assign PIDs to mother and infant • Assess eligibility
Behavioral and Counseling	
 • Provide HIV pre-/post-test counseling (if applicable) • Assess alcohol and drug use
Clinical	
 • Obtain medical and medications history • Perform complete physical examination • Perform obstetrical exam to assess fetal health • Assess TB symptoms, risk, and exposure • Gene Xpert, shielded chest x-ray, or sputum microscopy • Perform TST (if not available per medical record)
Laboratory	
Collect blood for:
 
 • IGRA (if not available per medical record) • Complete blood count (CBC) • Liver Function Tests • HIV-1 test (confirmatory tests as needed) • Coagulation profile

6.2 Mother Entry/Intensive PK Visit

The Entry Visit will be conducted over multiple days as a split visit. The administrative, regulatory, and clinical procedures should be conducted on the first day of the split visit; procedures that may provide information relevant to eligibility for the study (e.g., medical and medications history, physical examination, assessment of fetal movement and heart sounds) should be performed first, prior to final eligibility determination. In the event that a woman is found to be ineligible on the day of enrollment, enrollment should not occur.

Additional requirements for sequencing of procedures at the Entry Visit are as follows:

- Before enrollment:
 - Confirm final eligibility determination
 - Confirm the woman's continued consent for study participation
- After enrollment:
 - Prescribe study drug regimen
 - Provide meal
 - Perform first intensive PK blood draw
 - Administer study drug regimen (within 30 minutes after providing meal)
 - Complete remaining blood draws for intensive PK

Mother Entry/Intensive PK Visit Procedures (Day 0 and 72 hours following)	
Administrative and Regulatory	
 Review elements of informed consent and confirm woman's continued consent for study participation* Complete final eligibility determination and confirmation* Complete paper-based eligibility checklist*, enter checklist data into SES to enroll the mother-infant pair, print and file a copy of the confirmation file Provide meal within 30 minutes prior to administering study drug
Behavioral and Counseling	
 Signs and symptoms of active TB Counseling
Clinical	
 Assess TB symptoms, risk and exposure* Update medical and medications history* Perform targeted physical examination* Provide available findings/test results Record baseline AEs* Assess fetal movement and heart sounds*
Laboratory	Collect blood for: 
 Intensive PK sample collection CD4 count (HIV-1-infected only) HBsAG, HBsAb, HCV Ab
Study Product	
 Prescribe (according to local guidelines) study drug and administer RPT, INH, and pyridoxine under DOT

*Perform prior to enrollment

The Intensive PK sampling must be initiated on the same day (ideally in the morning) as the first dose of the study drug regimen, and conducted over the course of 72 hours according to the following time points: just prior to the first dose (t0), then 0.5h, 1h, 2h, 4h, 5h, 8h, 12h, 24h, 48h and 72h after the observed dose. Depending on site capacity, women may stay at the clinical research facility overnight after day 1 of the Entry Visit or return to the clinic at a designated time in the morning for administration of study drug and initiation of PK sampling. The same procedure can be followed for obtaining the PK samples at 48 and 72 hours after dosing.

Women will be asked to refrain from eating for two hours prior to each PK sampling dose of study drug, except for the meal provided by the site, which is to be eaten within 30 minutes before study drug administration. Women will be asked to refrain from further intake (except water) until three to four hours after the dose. The food type and quantity prior to each PK sampling dose will be recorded on CRFs.

RPT PK testing will be performed on all Intensive PK samples, after which, the t0 and 2h (or 4h) samples will be stored for later INH PK testing (see LPC for further details).

Women will be counseled about the signs and symptoms of active TB and asked to come to the clinic for an interim visit should any of the symptoms develop during the course of the study.

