RPT is well absorbed and reaches a peak concentration in non-pregnant adults approximately five hours after ingestion. Bioavailability is improved when ingested with food, though lipid content does not appear to impact the magnitude of this effect (30). In a substudy of TBTC 26, gender was not associated with variability in RPT PK parameters by population PK modeling (31). RPT's half-life ($t_{1/2}$) is five times longer than that of rifampin (11-18 hours versus 2-5 hours), resulting in measurable concentrations at and beyond 24 hours (32). Rifampin, a structurally similar rifamycin antibiotic, induces its own metabolism leading to reductions in half-life and AUC with repeat daily dosing. RPT also induces its own metabolism, but because of its longer half-life, accumulation occurs with multiple dosing (33, 34). RPT metabolism is not dependent on cytochrome P450. The effects of RPT on antiretrovirals' concentrations is currently under investigation, but, in ACTG 5279, no clinically significant reductions in efavirenz (EFV) concentrations were seen among 30 patients receiving daily RPT 10 mg/kg and isoniazid together with EFV-based combination ART (35). Preliminary results from a Phase I trial sponsored by Sanofi also demonstrated that once-weekly RPT did not reduce EFV concentrations appreciably, so it is likely that these drugs can be used safely together (36, 37).

EFV concentrations are marginally decreased among women in late pregnancy (38). However, few studies have evaluated this, and the numbers are small, largely because until recently, EFV was not used in pregnancy in many settings. EFV is now used without dose adjustment in pregnancy globally. There are no data about CYP2B6 activity among pregnant women taking EFV. Rifampin does not reduce EFV concentrations in pregnant women; in some women, INH increases EFV concentrations (depending on NAT2 genotype and CYP2B6 genotype).

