IMPAACT 2001 will be the first detailed study of the newer, shorter, and more tolerable regimen of RPT and INH with a focus on the metabolic alterations associated with pregnancy. The dose selected is the standard of care for adults based on TBTC 26 (see Section 1.2) and what is known about the metabolism of rifapentine in other populations (see Appendix II). This dose is expected to be appropriate for pregnant women as well.

The sampling strategy planned for IMPAACT 2001 is consistent with PK sampling in adults participating in TBTC trials of RPT, which will allow for comparison of the proposed IMPAACT 2001 study data with data from non-pregnant adults. Specifically, TBTC 26 used clearance as the main PK parameter, which will also be used as the primary PK parameter in IMPAACT 2001 for comparison with the non-pregnant historical controls (58). The sampling schedule is based on the expected PK profiles of RPT. The use of an intensive sampling strategy will support development of a model that estimates RPT PK well among pregnant women, including estimates for typical values and variability around absorption and elimination of the drug in this special population. The population PK modeling will be used to examine covariate effects (such as gestational age and weight) on PK parameters. With the sample size of 50 evaluable subjects, there will also be 90% power to detect one or more safety events for which the true rate of occurrence is 5 per 100 women or infants treated. The use of an interim analysis is a conservative approach, because there may be several different scenarios and variations in PK for RPT (e.g., changes in second trimester only, changes in third trimester only, similar changes in both trimesters, different changes in each trimester). With this approach, there will be power to detect all of them. To this end, a relatively large sample size is preferred to account for variability of the drug, itself, and possible physiologic differences between the second and third trimesters. Enrollment of half of each of the cohorts will provide sufficient power to detect a trimester-to-trimester effect.

The key limitations of using historical controls include the possibilities that controls and treated individuals (a) represent incomparable populations, and/or (b) differ systematically on key factors that affect the relationship between treatment and endpoint, and/or (c) encounter important differences in

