6.3 Mother Weekly Visit (On Study Drug Regimen), Sparse PK Visit

Women will have weekly study visits while on the study drug regimen. Requirements for sequencing of procedures at the weekly visits are as follows:

- Before administering study drug regimen:
 - Prescribe study drug regimen per site SOP
 - Provide meal

The PK sampling visits are ideally conducted in the morning. The Sparse PK sample collection will be conducted on the visit of the woman's last dose of the study drug regimen over the course of 48 hours according to the following time points: 1h, 4h, 24h, and 48h after the observed dose. Women who are still taking study drug and breastfeeding postpartum will express breast milk, and plasma samples will also be drawn at the following time points:

- First weekly visit after delivery, three hours after the study drug dose
- Second weekly visit after delivery, six hours after the study drug dose
- Last dose visit, 24 hours after the study drug dose (breast milk collection only)

Women will be asked to refrain from eating for two hours prior to each PK sampling dose, except for the meal provided by the site, which is to be eaten within 30 minutes before study drug administration. Women will be asked to refrain from further intake (except water) until three to four hours after the dose. The food type and quantity prior to each PK sampling dose will be recorded on CRFs.

RPT PK testing will be performed on all Sparse PK samples, after which, the 1h and 4h samples will be stored for later INH PK testing (see LPC for further details).

Mother Weekly Visit Procedures (7 ± 2 days apart)		
Administrative and Regulatory		
 • Provide meal within 30 minutes prior to administering study drug
Behavioral and Counseling		
 • Signs and symptoms of active TB Counseling • Assess infant feeding methods (postpartum only)
Clinical		
 • Perform targeted physical exam • Record/update medical and medications history • Record/update AEs • Provide available test results • Assess TB symptoms, risk and exposure • Assess fetal movement and heart sounds (until delivery)

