Laboratory	Blood	Collect blood for: 
 • Sparse PK sample collection (during the visit of the last dose and 48 hours following) • Plasma sample collection (breast milk PK participants only, conducted first and second week postpartum) • Complete blood count (every four weeks) • Liver Function Test (every four weeks) • Coagulation profiles (at one visit at ≥34 weeks gestational age only)
	Breast milk	Collect breast milk for: 
 • Breast milk PK sample collection (if eligible, conducted first and second week postpartum and on the visit of the last dose)
Study Product		
 • Prescribe (according to local guidelines) and administer RPT, INH, and pyridoxine under DOT

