Apparent clearance per kilogram body weight was significantly higher in children than adults. This relation was described by a maturation function, where clearance for the youngest child (age, 2 y) was 0.052 L/h/kg, decreasing to the fully matured value of 0.026 L/h/kg by older age (half-life, 1.5 y (38% RSE), resulting with fully matured value by approximately age 10). Relative bioavailability of rifapentine in fasting condition for higher doses, 900 mg and 1200mg compared to the lowest available dose in adults (600 mg) was found to be 0.96 (19% RSE) and 0.76 (16% RSE) respectively. Food increased relative bioavailability by 40% (8% RSE). Children who received crushed tablets had 26% (36% RSE) decreased relative bioavailability. There was no autoinduction with once-weekly dosing. Gender and race have also been investigated, and were not associated with rifapentine pharmacokinetics.

SUMMARY OF STUDY FEATURES

This population PK analysis evaluated data obtained from 4 clinical studies of rifapentine (TBTC Study 25, TBTC Study 26, children and adolescent study) (25, 63-65). A summary of the studies is provided in Table 1. PK profiles from a total of 227 subjects were used in this analysis.

Table 1. Summary of Studies Included in the Population PK Analysis

Study	Phase	n ^a	Population	Treatment	DrugX Dose
TBTC 25	I/II	35	Adult Patients with TB	RPT+INH	600mg, 900mg, 1200mg weekly
TBTC 26	III	157	Children and Adults with LTBI	RPT + INH	300- 900mg weekly
children	I	23	Children w/o TB	RPT	150mg, 300mg single dose
adolescent	I	12	Healthy Adolescents	RPT	450mg, 600mg single dose

^a Number of subjects receiving RPT included in the population PK analysis

TBTC Study 25

TBTC Study 25 was a prospective, double-blind, randomized Phase II trial to evaluate the tolerability of once-weekly, continuation phase, directly observed therapy with rifapentine at three doses (600, 900, and 1,200 mg) and of isoniazid in 150 HIV-seronegative patients with drug susceptible tuberculosis. The pharmacokinetic substudy included 35 adult patients with tuberculosis (continuation phase therapy) who received commercial formulation of rifapentine (600, 900, or 1200 mg once weekly), usually without food. Pharmacokinetic data were collected after ≥ 3 weeks of once-weekly treatment. Plasma samples for rifapentine and metabolite concentrations were collected (11 samples: baseline, 2, 4, 6, 8, 10, 12, 18, 24, 48, and 72 h after the dose) (65, 66).

TBTC Study 26 (PREVENT-TB Study)

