TBTC Study 26 was a Phase 3, randomized treatment trial of 8,053 patients with LTBI, comparing a 12-dose, once-weekly rifapentine and isoniazid regimen (3HP) to nine months of daily isoniazid (25). 161 patients were recruited into PK substudy from the Phase 3, PREVENT TB trial, of whom 157 had evaluable PK samples (80 children and 77 adults). Risk groups in the treatment trial were recent close contacts of pulmonary tuberculosis cases, HIV-infected persons, those with a recent tuberculin skin test conversion, or those with fibrotic or fibronodular abnormalities consistent with old, healed tuberculosis on chest radiograph. All patients had evidence of latent tuberculosis infection (e.g. positive tuberculin skin test) and no evidence of active tuberculosis. Children enrolled in this substudy were age 2 to 11 years and all children and adults in the PK substudy were treated with 3HP. Rifapentine was administered as 150 mg tablets. Rifapentine doses in children ranged from 300 to 900 mg based on weight and dosage (Table 2) and the rifapentine dose in adults was 900 mg (all patients weighed more than 45 kg). Children who could not swallow tablets were administered a suspension of crushed rifapentine and isoniazid tablets in either a soft food or liquid. Other foods consumed within two hours of drug administration were documented. For children, the once-weekly dosage of isoniazid was 25 mg/kg, (900 mg maximum), and adults were administered isoniazid 15 mg/kg (900 mg maximum) (25).

Table 2. Rifapentine dosing algorithm used for children in the PREVENT-TB study

Weight (kg)	Rifapentine dose (mg)	Rifapentine dosage (mg/kg)	Number of children in each group	Age of study patients (mean +SD in years)
10-14	300	21-30	34	2.6 \pm 0.8
>14-25	450	18-32	40	4.5 \pm 1.6
>25-32	600	19-24	7	7.4 \pm 2.2
>32-50	750	15-23	16	9.7 \pm 2.4
>50	900	<18	3	10.0 \pm 1.0

After at least three once-weekly doses of rifapentine and isoniazid, a single plasma sample collected 24-hours after administration of study drugs (C24) was used in the sampling protocol. A 2 mL venous blood sample for PK analysis was obtained 23 to 25 hours after drug administration and was processed according to standard procedures (67). Plasma concentrations of rifapentine and 25-des-RPT were determined using a validated high-pressure liquid chromatography assay (66).

Children study

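### Within-woman, postpartum and historical-control comparisons of rifapentine clearance mix pregnancy stage with dose number, and the planned model has no term to separate them

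*Protocol*

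**What the plan says.** **Timing in this trial.** Protocol 6.2 schedules eleven samples over 72 hours at entry: "The Intensive PK sampling must be initiated on the same day (ideally in the morning) as the first dose of the study drug regimen". Protocol 6.3 schedules four later samples (1, 4, 24 and 48 h): "The Sparse PK sample collection will be conducted on the visit of the woman's last dose of the study drug regimen". Breastfeeding women still on drug also give single plasma samples at the first two weekly visits after delivery; those too follow earlier doses.

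**Timing in the controls.** Section 1.3 states: "The sampling strategy planned for IMPAACT 2001 is consistent with PK sampling in adults participating in TBTC trials of RPT". Appendix II describes two adult sources. For the 35 adults of TBTC 25: "Pharmacokinetic data were collected after ≥ 3 weeks of once-weekly treatment". For TBTC 26, with 77 adults, sampling began "After at least three once-weekly doses of rifapentine and isoniazid, a single plasma sample collected 24-hours after administration of study drugs (C24". The only single-dose data are from 23 children and 12 adolescents aged 12 to 15.

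**Autoinduction.** Section 1.2: "RPT also induces its own metabolism, but because of its longer half-life, accumulation occurs with multiple dosing". Appendix II: "There was no autoinduction with once-weekly dosing".

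**Planned model.** Protocol 10.5 pools longitudinal and cross-sectional data and puts allometric scaling and gestational age on clearance and volume. Objective 2.2.2 lists gestational age, weight, age and HIV status as covariates. The SAP's stochastic model for rifapentine has between-subject variability and residual error only.

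**Interim rule.** Protocol 10.3 rests on the visit 1 intensive profiles. Under 10.3.2 a dose adjustment is discussed if median CL/F differs by more than 25% from the non-pregnant reference.

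**The concern.** Dose number and stage move together within each woman. Cohort 1 goes from second trimester at dose 1 to mostly third trimester at the last dose. Cohort 2 goes from third trimester at dose 1 to mostly postpartum. A model with a stage effect and no dose-number effect will credit any repeat-dose change in clearance to stage.

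Three results are exposed: the maintenance of drug levels between second and third trimester, which Protocol 9.1 calls the fundamental concern; the postpartum estimate of objective 2.2.1; and the interim comparison with controls, where dose 1 is set against repeated dosing for every adult. The consistency statement in Section 1.3 does not hold for dose number.

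**Working it through.** **1. The interim reference traces to Appendix II.** CL/F is 2.32 L/h at 70 kg with exponent 0.75, and food raises bioavailability by 40%.
- Fasting, 60 kg: 2.32 × (60/70)^0.75 = 2.07 L/h (Protocol 10.3.2: 2.07).
- Fed: 2.067 / 1.40 = 1.476 L/h (Protocol: 1.47, a 0.4% difference).

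The reference therefore comes from the dataset in which all 35 + 77 = 112 adults were sampled after at least three weekly doses.

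**2. Stage by dose.** With twelve consecutive weekly doses, the last falls 11 weeks after entry.
- Cohort 1: 14 + 11 = 25 to just under 28 + 11 = 39 weeks. Only women entering before 28 − 11 = 17 weeks are still in second trimester, a share of 3/14 = 21% if entry is uniform.
- Cohort 2: 28 + 11 = 39 to 34 + 11 = 45 weeks, so mostly after delivery.

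Expected profiles with 25 women per cohort (assumed: uniform entry, delivery at mean 39.5 weeks, SD 1.5):

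| | Second trimester | Third trimester | Postpartum |
|---|---|---|---|
| Dose 1 | 25 | 25 | 0 |
| Last dose | about 5 | about 22 | about 22 |

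Third trimester appears in both rows, so an additive dose effect can be estimated. The postpartum column has no dose 1 entry, and could not have one, because women must be pregnant to enrol.

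**3. Share of a repeat-dose effect absorbed by stage.** Take log CL/F with two occasions per woman, X_i = [1, third trimester, postpartum], z_i = last-dose indicator, and V = 0.40²J + σ²I. The 0.40 is the 40% inter-patient variability in Appendix II; σ, the inter-occasion SD, is assumed. When z is omitted, the bias per unit of dose effect is

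b = (Σ X′V⁻¹X)⁻¹ Σ X′V⁻¹z.

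Averaged over simulated entry and delivery weeks:

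| σ | Share into third vs second | Share into postpartum vs third | SE third vs second, without → with term | SE postpartum vs third, without → with term | SE of dose term |
|---|---|---|---|---|---|
| 0.1 | 0.92 | 0.94 | 0.03 → 0.05 | 0.03 → 0.05 | 0.04 |
| 0.2 | 0.80 | 0.87 | 0.06 → 0.08 | 0.06 → 0.09 | 0.07 |
| 0.3 | 0.69 | 0.80 | 0.09 → 0.11 | 0.09 → 0.12 | 0.10 |

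The shares are large because between-woman variability is large. The pooled fit then leans on within-woman change, which is the part tied to dose number.

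For scale, take an assumed 10% rise in clearance with repeated dosing, ln 1.10 = 0.095. At σ = 0.2 the trimester contrast shifts by 0.80 × 0.095 = 0.076 log units, about 8%, against an SE of 0.06.

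**4. The dose-1-only trimester comparison.** This contrast has no dose-number difference. Its SE is √(2 × (0.40² + σ²)/25) = 0.12, 0.13 and 0.14 at σ = 0.1, 0.2 and 0.3.

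**5. Interim reading.** Apparent ratio = true pregnancy ratio / (1 + x), where x is the assumed rise in clearance from dose 1 to repeated dosing.

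| True pregnancy effect | x = 0 | 5% | 10% | 20% |
|---|---|---|---|---|
| None | 0% | −5% | −9% | −17% |
| +30% | +30% | +24% | +18% | +8% |
| −20% | −20% | −24% | −27% | −33% |

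A true +30% falls to the 25% boundary at x = 1.30/1.25 − 1 = 4%.

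**The case against.** The strongest objection is that the premise may be false. Appendix II reports no autoinduction under this trial's weekly schedule, and then every bias above is zero. The dataset does bear on the question: it holds 23 single-dose children aged 2 to 12 beside 80 TBTC 26 children aged 2 to 11 sampled after at least three doses. It also puts clearance at its mature value by about age 10, which makes the single-dose adolescents informative about adults. This stands as evidence but is not conclusive. The comparison is across studies that differ in isoniazid use and food, no listed study describes sampling the same person at a first and a later dose, and no adult was sampled at dose 1. Section 1.2, for its part, gives no size for autoinduction under weekly dosing.

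A reader might infer that stage is wholly confounded with dose number, or that entry profiles are always a true first dose and later ones always the last. The documents do not support this. Second and third trimester are both sampled at dose 1 (Protocol 10.3), women who restart are enrolled as new participants (5.1.2), and the postpartum plasma samples precede the last dose.

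Four further limits stand:
- The 5, 10 and 20% values are assumptions, and the +30% example was chosen near the trigger.
- With 12 women, the SE of a median log clearance is about 1.25 × 0.40/√12 = 0.14, larger than a 10% shift. Crossing 25% prompts discussion and is not automatic.
- The working treats the 4-sample last-dose profile as precisely as the 11-sample entry profile. Noisier last-dose data would tend to lower the shares.
- The SAP permits more complex elimination models if necessary and plots residuals against time. That leaves room for a dose-number term but does not prespecify one.

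**Conclusion.** The point holds for three comparisons: the within-woman change across pregnancy, postpartum versus pregnancy, and the interim comparison with historical controls. For second versus third trimester the design can separate stage from dose number, but the planned pooled model does not use that.

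Without a dose-number term, about 70 to 90% of any repeat-dose change would enter the trimester contrast and about 80 to 94% the postpartum-versus-third contrast. These shares rest on 40% between-woman variability, 25 women per cohort, an assumed inter-occasion SD of 0.1 to 0.3, assumed entry and delivery distributions, and equal precision of the two profiles.

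A reader might go further and conclude that clearance does change with repeated weekly dosing, or that the interim decision will be wrong. The documents do not show either. They contain two statements on autoinduction that need reconciling, and no first-dose adult data in Appendix II to settle the matter. If clearance does rise with repeated dosing, the interim comparison would tend to hide a pregnancy-related increase and exaggerate a decrease.

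**What to change.** - **Protocol 10.5 and SAP.** Prespecify a first-versus-later-dose covariate on CL/F with inter-occasion variability, fitted to both cohorts together. Report the stage effects with and without it. State that the term assumes the same dose effect at every stage, which cannot be checked postpartum.
- **Sensitivity analysis.** Add a comparison of second with third trimester using the dose 1 profiles only.
- **Interim (10.3).** Show the 25% comparison under a stated range of assumed repeat-dose change, for example 0, 10 and 20%, as a sensitivity display only. A correction estimated from last-dose profiles would be weak at that point: they arrive about 11 weeks after entry, so few of the first 12 women may have one.
- **Text.** Qualify the consistency sentence in 1.3, and reconcile the autoinduction statements in 1.2 and Appendix II.

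The cost is wording and precision, with no added visits or samples. At inter-occasion SD 0.1, 0.2 and 0.3, the SE for third versus second trimester rises from about 0.03, 0.06 and 0.09 to 0.05, 0.08 and 0.11 log units. For postpartum versus third trimester it rises from about 0.03, 0.06 and 0.09 to 0.05, 0.09 and 0.12.
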